7.2 Subject Replacement

If a subject withdraws from the study after receiving DTX301, the subject will not be replaced. Subjects who withdraw from the study after signing the ICF, but before receiving DTX301, will be replaced and the replacement subject will be sequentially assigned to treatment with a new subject identification number.

8 Study Assessments and Procedures

8.1 Efficacy Assessments

Planned time points for all efficacy measurements in the study are listed in [Table 15-1](#).

8.1.1 Ureagenesis

The change from baseline in the rate of ureagenesis will be assessed at specified time points ([Table 15-1](#)). Planned time points for the collection of blood samples to determine the rate of ureagenesis are provided in Section 8.3.1. Subjects will fast for at least 6 hours, including liquids containing protein, sugar or carbonate, prior to administration of [1-¹³C]sodium acetate. After dosing, subjects will continue to fast for at least 4 hours. Water is allowed *ad libitum*. During Screening, assessment of rate of ureagenesis may be repeated if discrepant with subject's clinical status and severity.

Details for the preparation and shipment of samples are included in the ureagenesis manual and the laboratory manual.

8.1.2 Plasma Ammonia Area Under the Curve from Time Zero to 24 Hours

The change from baseline in plasma ammonia (AUC₀₋₂₄) will be assessed at specified time points ([Table 15-1](#)). Planned time points for the collection of blood samples to determine plasma ammonia (AUC₀₋₂₄) are provided in Section 8.3.2. Two samples will be collected at each time point for the plasma ammonia (AUC₀₋₂₄) determination. One sample will be sent to the local laboratory and 1 sample will be sent to the central laboratory. Details for the preparation and shipment of samples are included in the laboratory manual.

8.2 Safety Assessments

Planned time points for all safety assessments are listed in the Schedules of Events ([Table 15-1](#) and [Table 15-2](#)). Safety will be assessed based on AEs, SAEs, complete and targeted physical examination findings, vital sign measurements, ECG results, clinical laboratory assessments (clinical chemistry, plasma ammonia, hematology, urinalysis, and coagulation panel), viral shedding, measurement of neutralizing antibody titer to AAV8, measurement of AAV8 binding antibodies, and measurement of anti-OTC antibodies.

8.2.1 Physical Examination

A complete or targeted physical examination will be performed at the time points specified in the Schedule of Events (Table 15-1).

A complete physical examination will include assessments of the head, eyes, ears, nose, and throat; skin; and the endocrine metabolic, neurological, respiratory, cardiovascular, gastrointestinal, and musculoskeletal systems.

A targeted physical examination will include assessment of the skin and the respiratory, cardiovascular, and gastrointestinal systems.

Physical examination findings will be captured on the appropriate page in the eCRF.

8.2.2 Vital Sign Measurements

Vital sign measurements will be made at the time points specified in the Schedule of Events (Table 15-1). During the study, vital sign measurements are to be collected before any stimulating or anxiety-provoking procedures (eg, phlebotomy). Vital sign measurements will include heart rate, blood pressure (systolic and diastolic), and respiratory rate. Temperature will be included on days that the [1-¹³C] sodium acetate is administered (Screening, all inpatient visits and Week 20 outpatient visit). Height (at the Screening visit only) and weight will also be recorded.

- On Day 0, weight will be measured to ensure that the weight is within 10% of the screening weight used to calculate the dose of DTX301. Subjects with a confirmed change in weight that is > 10% from Screening should be further evaluated to exclude the presence of an acute condition or illness; if a benign explanation for the weight change is identified and documented, DTX301 can be given and dosed using the weight obtained on Day 0. **NOTE:** Any subject weighing > 100 kg (> 220 lb) will be dosed as if his or her weight is 100 kg.
- Vital signs should be measured with the subject having rested for at least 5 minutes beforehand. It is preferred that the measurement be late with the subject rested, rather than on-time with the subject not sufficiently rested. If the subject is not sufficiently rested, this needs to be stated in the source documents.
- On Day 1, vital signs will be measured at predose, approximately 5 minutes, and 0.5 (±5 minutes), 1 (±5 minutes), 2, 4, 6, and 8 hours (±15 minutes) after the start of DTX301 infusion. Vital signs will also be measured at approximately 22 hours (±1 hour) after the start of infusion, prior to subject discharge.

- It is acceptable for heart rate to be captured from the 12-lead ECG (Section 8.2.3).

Vital sign measurements will be recorded in the appropriate page in the eCRF. The medical monitor should be notified of any clinically significant changes or abnormal value in vital sign measurements (Section 9.1.2).

8.2.3 Electrocardiograms

An ECG will be performed at the time points specified in the Schedule of Events (Table 15-1).

- A single 12-lead ECG will be obtained at Screening, on Day 0 (baseline), at approximately 1 hour (± 15 minutes) after the start of infusion on Day 1, and at Week 52, using an ECG machine that automatically calculates the heart rate and measures PR, QRS, QT, and corrected QT intervals.

Twelve-lead ECGs should be measured with the subject having rested for at least 5 minutes beforehand. It is preferred that the measurement be late with the subject rested, rather than on-time with the subject not sufficiently rested. If the subject is not sufficiently rested, this needs to be stated in the source documents. Electrocardiogram results will be recorded in the appropriate page in the eCRF.

8.2.4 Clinical Laboratory Analyses

Laboratory tests, including LFTs and coagulation panel, will be closely monitored throughout the duration of the study. At any point between scheduled visits, additional, unscheduled assessment for LFTs, plasma ammonia, or any other biomarker to assess subject safety and clinical status may be performed, at the discretion of the investigator.

Investigators will receive flagged notification of any laboratory values that are outside of the normal range. Any abnormal laboratory test results (clinical chemistry, plasma ammonia, hematology, urinalysis, coagulation panel, or other laboratory parameters), including those that worsen from baseline or are felt to be clinically significant in the medical and scientific judgment of the investigator, are to be recorded as AEs or SAEs (Section 9.1.2).

However, any clinically significant safety assessments that are associated with OTC deficiency are **not** to be reported as AEs, **unless** they are judged by the investigator to be more severe than expected for the subject's condition.

Protocol: 301OTC01

All laboratory tests with results that are significantly abnormal during participation in the study should be repeated until the values return to normal or baseline. If such values do not return to normal within a period judged reasonable by the investigator, the etiology should be identified, and the sponsor notified.

Samples of blood, urine, saliva, and stool will be collected for study assessments. Any samples remaining at the end of the study may be stored for up to 15 years and analyzed to better understand the effect of DTX301 on OTC deficiency or other UCDs. The choice to allow retention and future analysis will be optional.

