3.2.7 Safety Stopping Criteria

Enrollment will be stopped, and the regulators will be notified if, at any time during the study, any of the following occur:

- Death of a subject following administration of DTX301
- An event with an intensity \geq Grade 3 (according to the Common Terminology Criteria for Adverse Events (CTCAE) [Section 9.1.3]), but excluding hyperammonemic crises (Section 3.2.6), develops following administration of DTX301
- Occurrence of a hepatic malignancy following administration of DTX301

Following DMC review when a stopping rule is met, if the decision is to restart enrollment, a substantial amendment will need to be approved by the regulatory authority.

Protocol: 301OTC01

Abnormal clinically significant laboratory values (clinical chemistry, plasma ammonia, hematology, urinalysis, and coagulation panel) as assessed by the investigator will be considered AEs. Laboratory values that meet any of the above criteria will result in a pause in enrollment until the DMC reviews the data and provide a recommendation for subsequent study conduct.

Any event that meets the above criteria will be reported immediately (within 24 hours) as outlined in Section 9.1.2.2 and the appropriate page(s) in the electronic case report form (eCRF) must be completed. Enrollment and dosing will be temporarily suspended until the situation can be assessed and risks to the subjects mitigated. The DMC will meet on an ad hoc basis if an investigator reports an AE/SAE that meets any of the study stopping criteria to review and assess the event. If study enrollment is suspended, all subjects who have been enrolled will remain in the study and will continue to be monitored through their completion or withdrawal from the study.

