9.1 Adverse Events and Serious Adverse Events

Adverse events will be assessed from the time the subject signs the ICF through the end of study/early withdrawal visit.

At every study visit, subjects will be asked a standard nonleading question to elicit any medically related changes in their well-being.

In addition to subject observations, AEs identified from any study data (eg, laboratory values, physical examination findings, ECG changes) or identified from review of other documents (eg, subject diaries) that are relevant to subject safety will be documented on the AE page in the eCRF.

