9.1.1 Definitions

9.1.1.1 Adverse Events

The investigator is responsible for reporting all AEs that are observed or reported during the study, regardless of their relationship to study product or their clinical significance.

Protocol: 301OTC01

An AE is defined as any untoward medical occurrence in a subject enrolled into this study regardless of its causal relationship to study product. Subjects will be instructed to contact the investigator at any time after the subject signs the informed consent if any signs or symptoms develop.

A treatment-emergent AE is defined as any event not present before exposure to study product or any event already present that worsens in either intensity or frequency after exposure to study product.

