9.1.2 Safety Reporting

9.1.2.1 Adverse Events

All AEs reported or observed during the study will be recorded on the AE page in the eCRF. Information to be collected includes drug treatment, dose, event term, time of onset, investigator-specified assessment of severity and relationship to study product, corticosteroid

Protocol: 301OTC01

regimen, [1-¹³C] sodium acetate, OTC deficiency, or hyperammonemia, time of resolution of the event, seriousness, any required treatment or evaluations, and outcome. Adverse events resulting from concurrent illnesses, reactions to concurrent illnesses, reactions to concurrent medications, or progression of disease states must also be reported. All AEs will be followed to adequate resolution. The Medical Dictionary for Regulatory Activities (MedDRA) will be used to code all AEs.

Any medical condition that is present at the time that the subject is screened but does not deteriorate should not be reported as an AE. However, if the condition deteriorates at any time during the study, it should be recorded as an AE.

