9.1.4 Assessment of Causality

The investigator’s assessment of an AE’s relationship to study product is part of the documentation process, but it is not a factor in determining what is or is not reported in the study. If there is any doubt as to whether a clinical observation is an AE, the event should be reported.

Protocol: 301OTC01

The relationship or association of the study product in causing or contributing to the AE will be characterized using the following classification and criteria:

- Unrelated:** This relationship suggests that there is no association between the study product and the reported event.
- Possible:** This relationship suggests that treatment with the study product is causing or contributing to the AE; ie, the event follows a reasonable temporal sequence from the time of the study product administration or follows a known response pattern to the study product but could also be produced by other factors.
- Probable:** This relationship suggests that a reasonable temporal sequence of the event with the study product administration exists and, based upon the known pharmacological action of the study product, known or previously reported adverse reactions to the drug or class of drugs, or judgment based on the investigator's clinical experience, the association of the event with the study product seems likely. The event disappears or decreases on cessation or reduction of the dose of study product.
- Definite:** This relationship suggests that a definite causal relationship exists between the study product administration and the AE, and other conditions (concurrent illness, progression/expression of disease state, or concurrent medication reaction) do not appear to explain the event. The event reappears or worsens if the study product is re-administered.

The relationship or association of corticosteroid regimen, [1-¹³C] sodium acetate, OTC deficiency, or hyperammonemia in causing or contributing to the AE will also be characterized using the classification terms above.

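### Protocol 8.2.4 conflicts with 3.2.7 and 9.1.2.1 on whether a worsening but expected OTC-associated finding is an AE, and SAP 9.1 does not settle it

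*Protocol*

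**What the plan says.** **Protocol 8.2.4** first requires abnormal laboratory results, plasma ammonia included, to be recorded as AEs or SAEs, and refers to 9.1.2. It then makes an exception, under which "any clinically significant safety assessments that are associated with OTC deficiency are" left out of AE reporting by default. The exception lapses only where "they are judged by the investigator to be more severe than expected", given that subject's disease. No grade or threshold defines expected.

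**Protocol 3.2.7** states: "Abnormal clinically significant laboratory values (clinical chemistry, plasma ammonia, hematology, urinalysis, and coagulation panel) as assessed by the investigator will be considered AEs". It has no exemption for OTC deficiency and no reference to 8.2.4.

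**Protocol 9.1.1.1** has the investigator report all AEs "regardless of their relationship to study product or their clinical significance". **Protocol 9.1.2.1** adds that AEs from "progression of disease states must also be reported". It exempts a condition present at screening that does not deteriorate, and requires it to be recorded if it does.

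**Protocol 9.1.4** asks for attribution beyond the study product: the relationship of the corticosteroid regimen, the labelled sodium acetate, "OTC deficiency, or hyperammonemia in causing or contributing to the AE will also be characterized" in the same categories.

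**Protocol 10.2 and Section 2** make the incidence of AEs, TEAEs and SAEs, by dosing cohort, the primary endpoint. **SAP 9.1** uses the general AE definition. It neither carries over the 8.2.4 exemption nor says how to treat events recorded under differing rules.

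**The concern.** Plasma ammonia is both the disease marker and a safety laboratory value, so the exemption bears on the measurement most likely to move if expression is inadequate or a scavenger taper does not hold. Scavenger adjustment may be considered after the Week 12 and Week 24 visits (Protocol 3.2.4), in an open-label study at approximately 20 sites. Suppose a subject's ammonia worsens after dosing and the investigator considers the rise clinically significant but in keeping with that subject's disease. A site working from 8.2.4 records nothing. A site working from 3.2.7 or 9.1.2.1 records an AE.

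What is at stake is whether the primary endpoint counts the same thing across sites and cohorts. With cohorts of two or three, one such event is a large share of the cohort. An analysis cannot restore an event that never reached the AE page.

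**Working it through.** The plan gives no figure to reproduce. The check is a comparison of the rules, then one line of arithmetic.

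**Step 1. Apply each rule to the same post-dose OTC-associated finding.**

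| Finding | 8.2.4 | 3.2.7 | 9.1.2.1 |
|---|---|---|---|
| Unchanged from pre-dose state | Not an AE | Silent on stability; an AE if clinically significant, read literally | Not an AE |
| Worse, and more severe than expected | AE | AE if clinically significant | AE |
| Worse, clinically significant, judged expected, not hospitalised | **Not an AE** | **AE** | **AE** |
| Hospitalised hyperammonemic crisis (HAC) | SAE under 9.1.1.2 | SAE under 9.1.1.2 | SAE under 9.1.1.2 |

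For stable findings 8.2.4 and 9.1.2.1 agree. The clash is in the third row. It is most direct between 8.2.4 and 3.2.7, because both address clinically significant safety findings and 3.2.7 names ammonia. The 9.1.2.1 entry assumes that a worsening ammonia value counts as deterioration of a condition present at screening.

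**Step 2. Can that row occur?** Inclusion criterion 5 admits subjects who historically cannot fully control ammonia, with pre-dose values below 200 µmol/L. Protocol 1.3.1 treats 100 µmol/L or more as clinically meaningful. Such a subject can rise above their own pre-dose level while the investigator still calls it expected. Under 3.2.4, two consecutive results of 100 µmol/L or more after a taper are grounds to consider reinstating scavengers, so an event that prompts that step could be absent from the AE count.

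**Step 3. Does anything settle it?** Sections 3.2.7 and 9.1 do not mention the exemption. Section 8.2.4 points to 9.1.2, whose test is deterioration, not severity beyond expectation. SAP 9.1 is silent.

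**Step 4. Size.** If one subject among n has such an event, the cohort's incidence of that event is 0/n under 8.2.4 and 1/n under 3.2.7, a difference of 1/n.

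- n = 3 (Cohort 1, Protocol 1.3.1): 1/3 = 33.3 percentage points.
- n = 2 (Cohort 4 as enrolled, SAP 3.1): 1/2 = 50 points.
- n = 18 (maximum enrolment): 1/18 = 5.6 points.

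These are movements in the incidence of that event. The proportion with any TEAE moves only if the subject has no other TEAE.

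**The case against.** The strongest reply is that 8.2.4 is a general rule followed by an express exception, and that a specific carve-out governs a general statement. On that reading the sentence in 3.2.7 merely introduces the enrolment pause. This is plausible, but 3.2.7 is itself specific, since it names plasma ammonia, and nothing in it or in 9.1 defers to 8.2.4. Two sites could reasonably read the documents in different ways.

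Several other replies stand and limit the point.

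- A reader might infer that all of 9.1 contradicts 8.2.4. It does not. The duty in 9.1.1.1 and the disease-progression sentence in 9.1.2.1 presuppose an AE; neither says that an OTC-associated value is one.
- A reader might infer that the exemption is needless because 9.1.4 already collects attribution. The entry criteria suggest a reason for it: without some exemption, a subject whose usual ammonia is raised could generate an AE at each draw.
- A reader might infer that the harm goes unseen. HACs are defined by symptoms, ammonia and medical intervention, not by admission, and have their own endpoint and eCRF page (specific collection followed Amendment 5, per SAP 8.3.2). Spot ammonia is taken at every post-dose visit in Table 15-1 and reported with the 24-hour results; AUC is a secondary endpoint; scavenger use is listed; and the DMC reviews longitudinal ammonia.
- A reader might infer that dose finding or the stopping criteria failed. The DLT definition does rest on AEs, but SAP 3.2.2 counts only the first 12 weeks, and scavenger tapering is considered only after the Week 12 visit. Section 3.2.7 also applies its criteria to laboratory values. A missed check is conceivable but not shown.

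Investigator judgement also enters 3.2.7, so aligning the rules makes recording consistent without making it objective.

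**Conclusion.** The inconsistency is real and confined to one class of event: an OTC-associated finding after dosing that is clinically significant, worse than the pre-dose state, judged expected, and not leading to hospitalisation. Within that class the protocol gives two answers, and neither it nor the SAP chooses between them. The AE and TEAE components of the primary endpoint are affected; SAEs for hospitalised HAC are not.

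The size is 33 points per subject in a cohort of three and 50 points in a cohort of two. It rests on the assumption that at least one such subject exists and that sites differ in the rule they follow. The documents give no frequency for such events, and a pooled range would not match an endpoint defined by cohort. They also do not show that any event was missed or that incidence is biased in a known direction between cohorts. The supported conclusion is that the primary endpoint's count is ambiguous at this boundary and that the ambiguity is cheap to remove.

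**What to change.** **Protocol.** Reconcile 3.2.7, 8.2.4 and 9.1 into one AE-recording rule. Limit the 8.2.4 exemption to OTC-associated findings that have not deteriorated from the subject's pre-dose state, the test 9.1.2.1 already applies to conditions present at screening. Cross-reference that rule from the laboratory-value sentence in 3.2.7. This keeps the exemption for subjects whose usual ammonia is raised. It concerns event recording only; treatment and enrolment-stopping rules are untouched.

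**SAP 9.1.** State the same rule and add two outputs.

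1. TEAEs with and without those attributed to OTC deficiency or hyperammonemia. SAP 9.1 says these attributions are collected, but its planned tables do not split by them.
2. A listing of post-dose ammonia values of at least 100 µmol/L that also exceed the subject's own baseline and have no matching AE. The baseline condition keeps values at a subject's usual level out. The listing is a prompt for medical review, not a definition of an AE.

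SAP 3.1 reports that Cohort 4 enrolment has ended, so rewording the protocol may not recover events already left unrecorded. The SAP items use data already collected and would show whether the exemption mattered.

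**Cost.** Protocol wording, one extra table split, one listing, and possibly slightly higher AE counts.

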8.2.4.1 Clinical Laboratory Parameters

The clinical laboratory parameters to be measured are listed in [Table 8-1](#). Samples are to be collected at the time points (± 5 minutes) specified in the Schedules of Events ([Table 15-1](#) and [Table 15-2](#)).

Protocol: 301OTC01

Table 8-1 Clinical Laboratory Parameters

| | |
|-----------------------------------|-------------------------------------------------------------------------------------------------------------------------------------------------------------------------------------------------------------------------------------------------------------------------------------------------------------------------------------|
| Clinical chemistry ^a : | Sodium, potassium, chloride, carbon dioxide, blood urea nitrogen, creatinine, glucose, calcium, phosphate, magnesium, albumin, total protein, creatine kinase, bilirubin (total, direct, and indirect), ALT, AST, ALP, gamma-glutamyltransferase, and lactate dehydrogenase |
| Spot ammonia | Plasma ammonia (STAT sample, local laboratory) ^b |
| Hematology: | Complete blood count with differential |
| Urinalysis: | Specific gravity, pH, glucose, protein, blood (by dipstick), ketones (by dipstick), and microscopic examination (if blood or protein is found) |
| Urine chemistry: | Orotic acid |
| Coagulation panel: | PT/INR, aPTT |
| Amino acid panel: | alanine, α -amino-butyric acid, arginine, asparagine, aspartic acid, citrulline, cystine, ethanolamine, glutamic acid, glutamine, glycine, histidine, homocysteine, hydroxyproline, isoleucine, leucine, lysine, methionine, ornithine, phenylalanine, proline, serine, taurine, threonine, tryptophan, tyrosine, and valine |
| Other ^c : | HBV surface antigen (HBsAg), HCV RNA, HIV |

Abbreviations: ALP, alkaline phosphatase; ALT, alanine aminotransferase; aPTT, activated partial thromboplastin time; AST, aspartate aminotransferase; HBV, hepatitis B virus; HCV, hepatitis C virus; HIV, human immunodeficiency virus; LFT, liver function test; PT/INR, prothrombin time/international normalized ratio.

- a. Through Week 12, one sample for LFTs is collected as part of clinical chemistry and sent to the central laboratory for analysis. A second sample for LFTs only is collected and sent to the local laboratory (STAT sample).
- b. Special handling is required for plasma ammonia. At Screening, prior to neuropsychological testing and prior to dosing with [1-¹³C]sodium acetate, a sample will be collected to confirm the subject’s plasma ammonia level. The subject’s plasma ammonia level should be < 100 $\mu\text{mol/L}$ or within the range of historical ammonia levels obtained when the subject was clinically stable (Section 4.1). If the ammonia level is inconsistent with the subject’s clinical status, the ammonia level may be repeated to ensure accurate results. If the subject is deemed clinically unstable, the assessments will be held until the subject is determined to be clinically stable. (Table 15-1). The study site may use the local laboratory sample from time 0 (prior to neuropsychological testing on Day 0 and at Week 52), and time 24 hour (prior to [1-¹³C]sodium acetate administration on Day 1 and at Weeks 6, 12, 24, and 52) from the plasma ammonia AUC₀₋₂₄ to confirm the subject’s plasma ammonia (Section 8.3.2).
- c. To be collected at Screening only.

Details for the preparation and shipment of samples will be provided by the central or specialty laboratory. Reference ranges for all parameters will be provided to the study site by the central or specialty laboratory.

A laboratory parameter may be repeated if there is any concern about the values obtained.

At any time after initiation of a prophylactic corticosteroid regimen, additional assessments of plasma ammonia levels, amino acid profiles, or any other biomarker to assess subject safety and clinical status may be performed, at the discretion of the investigator and as clinically indicated.

If additional nonprotocol-specified laboratory assessments are performed at the study site’s local laboratory and result in a change in subject management or the results are considered clinically

Protocol: 301OTC01

significant by the investigator (eg, SAE, AE, or dose modification), the results must be captured and sent to the sponsor along with other study data as defined in Section 9.1.2.

